6.10.1 Intra-Patient Escalation

A recent FDA review concluded that incorporation of a step dose / IPE can result in better patient tolerance of higher doses of CD3 bispecific molecules ([Saber, 2017](#)) due to a phenomenon of induced tolerance or tachyphylaxis. IPE regimens are used for the related ImmTAC molecule tebentafusp as well as the approved CD3 bispecific blinatumomab.

If the severity of cytokine-mediated AEs tend to become less severe following the initial doses of study drug using a fixed-dose regimen, the SST may initiate a 1-step IPE regimen, in which a lower dose is given on Cycle 1 Day 1 and a higher (target) dose is given on Cycle 1 Day 8 and beyond, as shown in [Figure 6-1](#).

[figure not shown]

Figure 6-1: Schematic Illustration of a 1-Step IPE Regimen

Rules for the 1-step IPE regimen are as follows:

- The initial target dose level must be a permitted escalation step based on BLRM output and the consensus of the SST
- The initial target dose level must not exceed the fixed-dose MTD (if established)
- The C1D1 dose level must be at least one dose level below the initial target dose, and must be a dose level that has been evaluated in ≥ 3 patients using a fixed-dose regimen, with a decision to escalate based on the BLRM output and SST review of all available relevant data.
- Escalation of the target dose in subsequent cohorts may proceed as in the main dose escalation:
 - Separate MTD/RP2D may be identified using fixed-dose and 1-step IPE regimens
 - DLT will be attributed to the dose level of the most recently administered dose prior to onset of the DLT (eg, a DLT with onset on C1D4 would be attributed to the C1D1 dose level, while a DLT with onset on C1D10 would be associated to the C1D8 dose level)
- The dose level for C1D1 remains fixed for all subsequent cohorts
- Patients receiving IPE must receive the C1D1 dose prior to receiving the target dose
- If a 1-step IPE regimen is evaluated in Phase I, it may be selected for further evaluation in Phase II

Experience with other CD3 bispecific molecules (including tebentafusp and blinatumomab) indicates that multi-step IPE may mitigate the risk of a cytokine-mediated AE more effectively than a 1-step IPE or fixed-dose regimen. If further mitigation of cytokine-mediated events is desired, the SST may decide to evaluate a two-step IPE regimen, in which an intermediate dose is given on Cycle 1 Day 8, as shown in [Figure 6-2](#).

[figure not shown]

Figure 6-2: Schematic Illustration of a 2-Step IPE Regimen

Rules for the 2-step IPE regimen are as follows:

- The initial target dose level must be a permitted escalation step based on BLRM output and the consensus of the SST
- The initial target dose level must not exceed the 1-step dose-escalation MTD (if established)
- The C1D8 dose level must be at least one dose level below the initial target dose, and must be a dose level that has been evaluated in ≥ 3 patients using a fixed-dose or 1-step IPE regimen, with a decision to escalate based on the BLRM output and SST review of all available relevant data
- Escalation of the target dose in subsequent cohorts may proceed as in the main and 1-step dose escalation:
 - Separate MTD/RP2D may be identified using fixed-dose, 1-step IPE, and 2-step IPE regimens
 - DLT will be attributed to the dose level of the most recently administered dose prior to onset of the DLT (eg, a DLT with onset on C1D4 would be attributed to the C1D1 dose level, while a DLT with onset on C1D10 would be associated to the C1D8 dose level)
- The dose levels for C1D1 and C1D8 remain fixed for all subsequent cohorts
- Patients receiving 2-step IPE must receive the C1D1 and C1D8 doses prior to receiving the target dose
- If a 2-step IPE regimen is evaluated in Phase I, it may be selected for further evaluation in Phase II

An example of how IPE might be implemented is shown in [Figure 6-3](#).

[figure not shown]

Figure 6-3: Representative Escalation Path Incorporating IPE

IPE = intra-patient escalation.

Actual dose levels will be determined using BLRM and must be approved by SST. In this scenario, after 3 patients were enrolled in Cohort 4 and completed DLT evaluation, the recommended next dose per BLRM was 195 mcg. The SST determined that the 195 mcg dose would be better tolerated using a 2-step escalation regimen, and so Cohort 5 was opened with a dose of 30 mcg on C1D1, 100 mcg on C1D8, and 195 mcg as the target dose (weekly starting on C1D15).

In addition, a patient who is enrolled in a lower dose cohort may move to a higher dose cohort once all the following criteria are met:

- The patient has completed at least 3 cycles of treatment
- The patient did not experience any DLT or any \geq Grade 3 treatment-related toxicity
- The patient does not have any ongoing \geq Grade 2 treatment-related toxicity
- The higher dose cohort has completed SST review with a decision to escalate or was determined to be the MTD/RP2D

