6.2 Treatment Regimen and In-Patient Hospitalization

Patients enrolled in this study will receive treatment with single-agent IMCnyeso dosed weekly on Days 1, 8, 15, and 22 of each 4-week cycle. All dosages prescribed and dispensed to patients and all dose changes during the study must be recorded on the Dosage Administration Record and electronic case report form (eCRF).

For each administration of study medication, a physician must be present at the site or immediately available to respond to emergencies. Study sites will be instructed on the conservative management of symptoms associated with CRS (eg, hypotension), as described in [Section 6.15](#). Fully functional resuscitation equipment and medications to handle acute infusion-related emergencies (eg, anaphylaxis, CRS) must be available at each study site.

Patients will be hospitalized for 2 nights following the administration of the first dose (C1D1) of IMCnyeso and will remain at the site for overnight observation following administration of the second dose (C1D8). In addition, patients receiving intra-patient escalation (IPE) will be hospitalized overnight following the first three doses (C1D1, C1D8, and C1D15). After reviewing safety, PK, and cytokine data from at least 3 patients enrolled at a given dose level, the SST may decide that 1 night of hospitalization is adequate after the first dose for subsequent

patients (with longer hospitalization if indicated). After Phase I is completed and the SST has reviewed all available relevant data for at least 6 patients at the RP2D, the SST may decide to reduce the minimum required monitoring time during the Phase II portion of the study to no less than 8 hours post-end of infusion on C1D1, C1D8, and/or C1D15 (with longer hospitalization if clinically indicated). Patients who experience certain AEs may require additional in-patient monitoring as described in [Section 6.15](#).

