6.4 Study Drug Administration

For each patient, the first dose will be infused over 2 hours (± 15 minutes); for dose levels ≤ 30 mcg; the first dose may be infused over 1 hour (± 10 minutes). If the first dose is well tolerated without \geq Grade 2 infusion and/or a hypersensitivity reaction, a given patient's subsequent infusion times may be reduced to 1 hour (± 10 minutes) starting at C1D8, and further reduced to 30 minutes (± 10 minutes) starting at C3D1 provided the above conditions continue to be met. Investigators may prolong the infusion time for individual patients if medically indicated at any time.

The entire contents of the IV bag will be administered using an infusion pump. A further 30 mL of 0.9% sodium chloride should be used to flush the line after the IMCnyeso solution has been infused. The infusion rate should not be changed, unless necessary to manage acute reactions. If the line is not flushed, this must be documented.

The initial dosing of patients in the dose-escalation cohorts will be staggered, with at least a 1-week interval between the first 2 patients at each dose level. The IRS will be used to control

patient allocation to treatment and ensure the dosing intervals and cohort recruitment complies with the protocol.

Please refer to [Section 6.12](#) for guidance regarding pre-medication and interruption of anti-hypertensive medications around the time of each dose.

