6.9 Starting Dose Rationale

The rationale for the QW dosing regimen in this study are based on the proof-of-concept clinical study of tebentafusp where manageable toxicity was observed with QW dosing of tebentafusp, as well as single-agent anti-tumor activity in both uveal and cutaneous melanoma.

IMCnyeso is a highly human-specific fusion protein. Neither the anti-CD3 nor the TCR portions cross react with any of the standard toxicology species, as discussed in [Section 1.3](#). Therefore, there is no relevant toxicology species to enable the setting of a starting dose using the conventional no adverse effect level (NOAEL) method. In the absence of a relevant toxicology species, MABEL, with receptor occupancy calculations, was used to set a safe starting dose. Derivation of the first clinical dose using the MABEL is shown below.

In vitro pharmacology assays measuring the efficacy of IMCnyeso against cancer cell lines were used to define the MABEL. In these assays, human T cells were added to target cells with different concentrations of IMCnyeso to determine the effects of cytokine release and killing induced at the given concentrations of IMCnyeso. The target cells used were HLA-A*02:01 positive and NY-ESO-1 positive cancer cells, which in the presence of IMCnyeso, induce the CD3 positive effector T cells in the PBMC population to both release IFN- γ and kill the tumor cells. In general, IFN- γ release is observed at IMCnyeso concentrations that are lower than the concentrations required for the observation of target-cell killing. Based on the killing assays and IFN- γ release assays, the MABEL observed in the in vitro assays for IMCnyeso is 5 pM.

The acceptable starting dose in the Phase I dose-escalation study is defined as the IV dose of IMCnyeso with a predicted C_{max} of serum at the MABEL (5 pM) and a receptor occupancy between 10%–30% at C_{max} . The use of C_{max} as the PK determinant of the starting dose prediction is based on the observed toxicity profile of the first ImmTAC in the clinic, tebentafusp, where it was observed that the related and more severe toxicities are observed in the immediate hours following dosing, when the concentration of tebentafusp was maximal. These data suggest that toxicity is related to the maximal plasma concentration more than the overall exposure or the area under the curve (AUC).

Thus, the determination of the starting dose is as follows:

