6.10 Dose-Escalation Decision Making

Dosing will begin with the first cohort at the starting dose of 3 mcg QW (Table 6-2). All doses administered to subsequent cohorts of patients will be determined by the SST and will be guided by the BLRM and will be subject to both the EWOC principle and the escalation rule.

Dose-escalation decisions will be made by the SST, which will consist of the Study Investigators, the Sponsor Medical Monitor, and a statistician. For each cohort, dose escalation or de-escalation decisions will be based on the SST's review of all relevant data available, from all dose levels evaluated in the ongoing study, including safety information, DLTs, all \geq Grade 2 toxicity data, PK, and pharmacodynamic data from evaluable patients (as defined in Section 6.10.2). The data and BLRM dose recommendations will be discussed and agreed upon during the dose-escalation teleconference (DETC), and all decisions will be documented in the meeting minutes and shared with all participating Principal Investigators.

If toxicity resolves following appropriate management and provided treatment discontinuation criteria are not met (see Section 6.16), patients experiencing DLTs may continue treatment with IMCnyeso only after agreement with the Sponsor Medical Monitor. With each dose cohort in Phase I, determination of the next dose to be tested in the dose escalation will be guided by the BLRM. Decision making will be based on all evaluable patients in the dose-determining set (DDS) at each cohort level (see Section 6.10.1). At each decision point, the BLRM provides an estimate of all dose levels of IMCnyeso that do not exceed the MTD and incorporates all DLT information at all dose levels for this estimation (see Section 9). In general, the next dose will have the highest chance that the true DLT rate will fall in the target interval (16%–33%) and will always satisfy the EWOC principle. In all cases, the dose for the next cohort will not exceed a 3.34-fold increase from the previous dose. Smaller dose increases may be recommended by the

Investigators and Sponsor upon consideration of all available clinical data. Further details of the BLRM including additional simulated escalation pathways are provided in [Section 13.3](#).

The estimated dose levels to be tested in this study (in the scenario that no DLT are reported) are shown in [Table 6-2](#). Actual doses will be determined using the BLRM and must be agreed upon by the SST.

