6.10.2 Definition of DLT-Evaluable Patients for the Dose-Determining Set

Patients are considered as DLT-evaluable if they meet one of the following criteria:

- Experienced a DLT during the 28-day DLT evaluation period, **OR**
- Did not experience a DLT during the 28-day DLT evaluation period, received at least 3 of the 4 planned doses of IMCnyeso (including at least 2 doses at the target dose level), and were observed for \geq 28 days following the first dose

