ECOG performance status	X											X					D1 of each cycle	
Hematology panel	X	X	X	X	X	X	X	X	X	X	X		X				D1 of each cycle	
Chemistry panel	X		X		X	X	X	X	X	X	X		X				D1 of each cycle	
Thyroid function	X						X				X							
Urine pregnancy test (women of childbearing potential)	X						X				X						D1 of each cycle	
PK and Immunogenicity																		
Pharmacokinetic sampling	8x	3x	8x	X	4x	4x	2x		2x		2x		2x			2x on D1 of odd-numbered cycles		
Immunogenicity sampling	X		X		X		X				X						D1 of odd-numbered cycles	
Disease Assessment																		
CT/MRI scans and disease assessment												X				Q8W to W40 (C3, C5, C7, C9, C11), then Q12W (C14, C17, etc)		
Tumor biopsy	Between C1D9 and C1D16 (required for ≥ 10 patients in Phase II, optional for all other patients) Optional for all patients at time of progression																	

IMCnyeso administration	X		X		X	X	X	X	X	X	X	X	X	X	D1, D8, D15, and D22 of each cycle
-------------------------	---	--	---	--	---	---	---	---	---	---	---	---	---	---	------------------------------------

AE = adverse event; C#D# = Cycle # Day #; [REDACTED]; CT = computerized tomography; ECG = electrocardiogram; ECOG = Eastern Cooperative Oncology Group; EOI = end of infusion; hr = hour(s); min = minutes; MRI = magnetic resonance imaging; [REDACTED]; PK = pharmacokinetics; Q#W = every # weeks; [REDACTED]; W = week.

ECG assessments are to be done pre-dose and within 1 hour of EOI on indicated days.

Vital signs (body temperature, pulse, respiratory rate, and blood pressure; in addition, oxygen saturation should be collected for \geq first 3 cycles of treatment) are to be assessed at the following timepoints:

- C1D1/C1D2 and C1D8/C1D9: pre-dose (within 2 hours), EOI (within 15 min), every 2 hours (\pm 15 min) through 12-hour post-EOI, every 4 hours (\pm 30 min) until discharge
- All other doses: pre-dose (within 2 hours), EOI (within 15 min), and 1-hour post-EOI (\pm 15 min)

Pharmacokinetics samples are to be collected at the following timepoints:

- C1D1 and C1D8: pre-dose (within 2 hours), EOI (within 15 min), 1-hour post-EOI (\pm 15 min), 2-hour post-EOI (\pm 15 min), 4-hour post-EOI (\pm 15 min), 6-hour post-EOI (\pm 30 min), 8-hour post-EOI (\pm 1 hr), and 12-hour post-EOI (\pm 3 hr)
- C1D2: 24-hour post-EOI (\pm 4 hr), 36-hour post-EOI (optional, \pm 4 hr), and 48-hour post-EOI (optional, \pm 4 hr)
- C1D9: 24-hour post-EOI (\pm 4 hr)

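### No rule says whether the first-dose and Cycle 1 safeguards, or the DLT period, restart when a patient moves to a higher-dose cohort after three or more cycles

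*Protocol*

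**What the plan says.** Protocol Section 6.10.1 states that "a patient who is enrolled in a lower dose cohort may move to a higher dose cohort once all the following criteria are met". There are four criteria. One is timing: "The patient has completed at least 3 cycles of treatment". Two concern tolerance: no DLT and no related toxicity of Grade 3 or higher so far, and no related Grade 2 or higher toxicity still ongoing. The fourth is that the SST has cleared the receiving cohort for escalation, or that it is the MTD/RP2D. Infusion time, admission, monitoring, sampling and DLT observation are not mentioned.

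The rules that could govern the first higher dose are elsewhere:

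- **Infusion (6.4).** Two hours applies to a patient's first dose, with 1 hour allowed at 30 mcg or below. Thirty minutes is allowed "starting at C3D1 provided the above conditions continue to be met".
- **Admission (6.2).** "Patients will be hospitalized for 2 nights following the administration of the first dose (C1D1) of IMCnyeso", then overnight after C1D8 and, for intra-patient escalation (IPE), after C1D15.
- **Vital signs (Table 7-2 footnote).** The long series belongs to C1D1/C1D2 and C1D8/C1D9. For the rest: "All other doses: pre-dose (within 2 hours), EOI (within 15 min), and 1-hour post-EOI".
- **Cytokines and PK (Table 7-2 footnotes).** The last scheduled cytokine samples are at C3D1. After Cycle 3, PK is taken only on Day 1 of odd-numbered cycles.
- **DLT evaluability (6.10.2).** A patient counts who "Experienced a DLT during the 28-day DLT evaluation period", or who had no DLT, received enough doses and was observed for 28 days from the first dose. Section 6.12 lets the SST count later events.
- **SAP.** Section 4.2.1 promises a listing of escalated patients and shows them once per cohort, but only in baseline-data summaries. Section 4.3.3 classifies safety patients by the treatment they started on.

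**The concern.** The protocol treats first exposure to a dose level as the risky moment and puts its slow infusion, hospital stay and dense sampling there. Section 6.9 adds, from the related molecule, that "toxicity is related to the maximal plasma concentration more than the overall exposure". A patient who moves up also meets a dose level for the first time, but by the calendar is long past every date that triggers those measures. Read literally, the first higher dose could be given with the shortest infusion and least scheduled observation in the study.

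There is also a data problem. The dose model is fed by DLTs in a window counted from the patient's first dose. A mover has normally already contributed a no-DLT record at the lower dose. No rule says whether a later reaction, or an uneventful course, at the higher dose is counted, or at which dose. If events are added case by case while uneventful movers are not, the numerator and denominator at that dose no longer match. In the safety tables, classification by initial treatment can place a reaction at the higher dose under the lower one.

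**Working it through.** The plan states no figure on this point to reproduce. The check is to place the earliest permitted move on the calendar and read off which rules apply, **assuming that cycle numbering continues**.

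**1. Timing.** Three cycles of 28 days (Section 7.2) end on Day 84, so the earliest move is Day 3 × 28 + 1 = 85, which is C4D1, after 3 × 4 = 12 planned weekly doses. That is past C3D1, from which 30 minutes is allowed, and 85 − 28 = 57 days beyond the end of the DLT period.

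**2. Scheduled safeguards.**

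| Item | First dose (C1D1/C1D2, main schedule) | First higher dose at C4D1 |
|---|---|---|
| Infusion | 2 h (1 h allowed at ≤ 30 mcg) | 30 min allowed if prior infusions tolerated |
| Required admission | 2 nights (SST may reduce to 1) | none stated |
| Vital-sign time points | about 14 | 3, last at 1 h after infusion |
| PK samples | 8, plus up to 3 on C1D2 | 0 |
| Cytokine samples | 4, plus 1 on C1D2 | 0, unless CRS is suspected |
| 28-day DLT period | running | ended |

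ECG, hematology and chemistry are still scheduled at C4D1. A move at C5D1 would bring two PK samples, before dosing and at end of infusion.

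**3. Infusion rate.** Rate = dose / time. At 100 mcg, 100 / 0.5 = 200 mcg/h against 100 / 2 = 50 mcg/h. The ratio is 4 at any dose.

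**4. Effect on peak level (illustrative).** For a constant infusion over T hours in a one-compartment model, the end-of-infusion level is proportional to (1 − e^(−kT)) / (kT), with k = ln 2 / half-life. The human half-life is not given as a figure beyond being under 24 hours; Section 6.9 gives 2–3 hours in mice, so the half-lives below are assumptions.

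| Assumed half-life | 30 min vs 2 h |
|---|---|
| 2 h | 0.918 / 0.721 = 1.27 |
| 3 h | 0.944 / 0.801 = 1.18 |
| 6 h | 1.09 |
| 12 h | 1.04 |
| 24 h | 1.02 |

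The peak rises by about 2% to 27%. That is modest; the larger difference is in observation (step 2).

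**5. Does numbering continue?** The protocol does not say. SAP Section 4.2.1 speaks of patients enrolling in more than one cohort, Section 6.2 allows for baseline values that differ between cohorts, and Sections 7.1 and 7.2.1 refer to an initial C1D1 dose. This wording is compatible with a second C1D1, but no reset rule is written. Under a restart the scheduled safeguards would return. DLT evaluability would still need clarifying, because Section 6.10.2 counts its 28 days from the first dose.

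**6. Where the event is counted.** Section 6.12 leaves late events to the SST. Section 6.10.1 attributes a DLT to the most recent dose before onset, but as a rule of the 1-step and 2-step IPE regimens, not of cohort moves. SAP Section 4.3.6 says that the dose-determining set uses actual dose received, but its entry criteria remain the 28-day ones. In the Phase I safety tables, Section 4.3.3 keeps the patient in the starting group.

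**The case against.** The strongest reply is that the mover is a low-risk patient at a cleared dose. The patient has completed three cycles without a DLT or related Grade 3 toxicity, the SST has reviewed the receiving dose, and Section 6.10.1 itself relies on induced tolerance after earlier doses. The 30-minute infusion is optional and depends on prior tolerance, and investigators may prolong any infusion. Reactive safeguards remain: admission for CRS from Grade 1 (Table 6-4), 24-hour notification from Grade 2 (Section 8.5), and extra cytokine samples when CRS is suspected. Keeping pre-exposed patients out of a first-28-day model is also defensible. The SAP's Safety RP2D set (4.3.4) would include a mover who reaches the RP2D, although those combined outputs are optional.

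Most of this stands and limits the point. It does not close the gap: discretion is not a rule, and sites could handle movers differently.

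A reader might infer more than the documents support:

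- **A 100-fold step, from 3 mcg to the 300 mcg target of SAP cohort 7.** That cohort is a 2-step regimen, and Section 6.10.1 requires its C1D1 and C1D8 doses before the target.
- **A breach of the escalation cap.** The text is "the dose for the next cohort will not exceed a 3.34-fold increase from the previous dose". It limits new cohorts, not one patient's change of dose.
- **Reactions at 4–24 hours that would be missed.** Section 1.4 reports this timing for tebentafusp after its first two or three doses; a mover is at about the thirteenth dose.
- **The same gap for IPE target doses.** Overnight stays and Table 13-13 cover these within the 28-day period; only a modest difference in infusion time is left.

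**Conclusion.** The gap is real. The rules permit, and do not guard against, a first higher dose after a cohort move given over 30 minutes (four times the 2-hour rate), with no required admission, three vital-sign checks ending at 1 hour, no scheduled cytokine sample and, at C4D1, no PK sample. A severe reaction then falls outside the standard DLT period and may be tabulated under the lower starting dose. In a first-in-human trial with CRS as an adverse event of special interest, this is a safety weakness and not only missing detail.

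It should not be read as saying that movers will be treated this way, or that their reactions can never count as DLTs: the infusion time is a choice, and Section 6.12 gives the SST power to count late events. The conclusion assumes that cycle numbering continues, which the documents leave open, and the peak-level figures rest on assumed half-lives and a simple model. How many patients would move is not stated.

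**What to change.** Reconcile Protocol Section 6.10.1 with 6.2, 6.4, 6.10.2, 6.12 and Table 7-2, and with SAP 4.2.1 and 4.3.3:

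1. State whether Cycle 1 rules restart at a cohort move. If not, state which of them (infusion time, admission, vital signs, laboratory, PK and cytokine sampling) apply at the first administration of the higher dose. The clinical team must choose the rule; none is proposed here.
2. State whether the SST reviews post-move toxicity as DLT information, at which dose level, and whether a mover without an event also contributes to the dose-determining set at that dose.
3. In the SAP, tabulate post-move adverse events by the dose received at onset, and keep the planned listing.

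The cost is amendment wording, a small addition to the safety tables, and possibly more observation for the few patients who move.
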